2.2. Violations and Deviations

Violations of entry criteria will be reported to the Data Safety and Monitoring Board (DSMB).

3.0. PRIMARY, SECONDARY AND TERTIARY AIMS

Primary Aim

- a. To determine in a randomized, double-blind, placebo-controlled setting whether LDM given at a target dose of 15 to 20 mg po weekly will reduce rates of recurrent myocardial infarction, stroke, or cardiovascular death among patients with a prior history of myocardial infarction and either type 2 diabetes or metabolic syndrome.

Secondary Aims

- a. To determine in a randomized, double-blind, placebo-controlled setting whether LDM will reduce rates of all-cause mortality among patients with a prior history of myocardial infarction and either type 2 diabetes or metabolic syndrome.
- b. To determine in a randomized, double-blind, placebo-controlled setting whether LDM will reduce rates of the primary endpoint plus coronary revascularization.
- c. To determine in a randomized, double-blind, placebo-controlled setting whether LDM will reduce the rates of hospitalization for congestive heart failure.
- d. To determine in a randomized, double-blind, placebo-controlled setting whether LDM will reduce rates of the primary endpoint plus all-cause mortality plus coronary revascularization plus congestive heart failure.
- e. To determine in a randomized, double-blind, placebo-controlled setting the side effect profile of LDM in a non-rheumatologic population at risk for recurrent vascular events. By so doing, CIRT will evaluate the net clinical benefit or harm that might accrue from the hypothesized use of LDM as a novel method for the secondary prevention of myocardial infarction, stroke, and cardiovascular death.
- f. To determine in a randomized, double-blind, placebo-controlled setting whether LDM will reduce the rate of new onset type 2 diabetes among those with metabolic syndrome but not diabetes at study entry.

Tertiary Aims

In addition, we will determine in a randomized, double-blind, placebo-controlled setting whether LDM will

- a. reduce rates of the individual components of the primary endpoint
- b. reduce rates of the primary endpoint plus unstable angina requiring unplanned coronary revascularization
- c. reduce rates of coronary revascularization
- d. reduce rates of peripheral artery disease
- e. reduce rates of symptomatic deep vein thrombosis or pulmonary embolism, including those considered to be provoked and those considered to be idiopathic
- f. reduce rates of clinically significant aortic stenosis
- g. reduce rates of atrial fibrillation
- h. have positive or negative effects on standardized measures of quality of life and global health status

Proposed Exploratory and Mechanistic Studies

Clinical endpoints of interest that will be prospectively evaluated include incident age-related macular degeneration, sleep apnea, and nephropathy and retinopathy. In addition, a plasma and DNA bank will be established as part of the trial protocol. Thus, cohort accrual and biobanking also allows for the evaluation of several exploratory aims that relate to mechanisms of effect using measured plasma biomarkers of inflammation and glucose metabolism, as well as potential genetic determinants of LDM activity. Analyses are planned that will

- a. Evaluate the effect of LDM as compared to placebo on a series of inflammatory biomarkers such as IL-6, TNF, CRP, interleukin-1 (IL-1), and interleukin-1 receptor antagonist (IL1ra), and to ascertain whether any effects on these biomarkers mediate observed benefits or risks of LDM on clinical outcomes in the trial.
- b. Evaluate whether genetic polymorphisms associated with vascular risk, inflammation, thrombosis, or LDM metabolism modify any benefits or risks of LDM on clinical outcomes observed in the trial.
- c. Among subjects with baseline diabetes, evaluate the effect of LDM as compared to placebo on indices of diabetic progression and glycemic control such as need for diabetes treatment intensification, proportion of subjects achieving optimal glycemic control (HbA1c<7.0%), and change in HbA1c overall and by study visit.

Variables for safety assessment will include:

- a. adverse events
- b. transaminase levels
- c. hematology
- d. creatinine clearance
- e. reported symptoms

4.0. ANALYSIS METHODS

4.1. General Principles

In the analysis of efficacy, subjects will be grouped by the treatment to which they were randomized. In the analyses of safety, subjects will be grouped by the treatment received.

All analyses will be stratified by time since the confirmed index myocardial infarction (≤ 6 months vs > 6 months) as well as presence of diabetes or metabolic syndrome at entry.

4.2. Demography

The following will be reported on all randomized subjects: age, sex, race, weight, height, BMI, waist circumference, medication use, vital signs, CHD risk factors, education, exercise, alcohol consumption, revascularization status, and significant medical history. We will also collect information on other risk factors for recurrent cardiovascular events, such as severity of the index event, functional status, and relevant comorbidities. For continuous variables (e.g. age), the mean, standard deviation (SD), minimum, maximum, and n will be presented. For categorical variables (e.g sex), frequency counts and percentages in each category will be

provided. Data will be given by center, treatment, and subject. The randomized design and large sample size of CIRT should provide balanced distributions of baseline characteristics between the two treatment groups. Nonetheless, initial analyses will be conducted to identify any chance imbalances in these distributions using Wilcoxon rank-sum tests for continuous variables and Chi-square tests for categorical variables. These hypothesis tests are intended for data monitoring and quality control, and not to determine which baseline covariates to include in efficacy analyses³. In particular, these analyses will form part of the routine monitoring of the trial and will be regularly reported to the Data and Safety Monitoring Board.

4.3. Efficacy

Efficacy analyses of the primary and secondary endpoints of the trial will focus on time from randomization to the first occurrence of the event. These analyses will use a likelihood ratio test based on a proportional hazards model stratified on time since index myocardial infarction (≥ 6 months vs < 6 months) and diabetes mellitus vs metabolic syndrome alone at baseline, to test the null hypothesis of no association between assignment to active methotrexate and the rate of the endpoint. Estimation will use the exact method to handle ties⁴. Although randomization is also stratified by site, we judge the potential loss of information associated with additional stratification on this variable to be a greater concern than any associated gain, so that stratification by site will not be part of the primary analysis. All primary and pre-specified secondary analyses will classify patients according to their randomized treatment assignment, i.e. according to the intention to treat principle, and will base evaluation of statistical significance on a two-sided test with level 0.05. The estimated relative hazard in the methotrexate group compared to the placebo group with an accompanying 95% confidence interval will quantify the treatment effect⁵. If this relative hazard is less than 1, then $100 \times (1 - \text{estimated relative hazard})$ will be defined as the percent reduction in hazard associated with methotrexate treatment.

Rates of occurrence of the endpoint will be defined as the total number of subjects who have this event in a treatment group per 100 person-years of follow-up, counting all time from randomization until the first of the event, death, end of trial, or withdrawal of consent. The primary analysis will estimate the probability of the endpoint by time after randomization within treatment groups based on the method of Kaplan and Meier⁶. As an additional analysis, we will also use the proportional hazards model to control for baseline factors that might influence the rate of the endpoint (e.g. age, race, gender, severity of index event, baseline comorbidities, and concomitant medications), as control for these variables may yield more efficient estimates of relative treatment effects⁷. However, these analyses are secondary, and the logrank test, stratified on time since index MI and baseline diabetes without adjustment for covariates, is the pre-specified, primary analytic approach. If Kaplan-Meier plots of event free survival by study time, or related plots of $\log(-\log)(\text{survival})$, indicate violations of the proportional hazards assumption, or a formal test of trend in the scaled Schoenfeld residuals indicates such a violation⁸, then weighted log-rank tests will be used according to strategies described by Pecková and Fleming⁹. However, even in the presence of an apparent violation of the proportional hazards assumption, the analysis described above gives a valid (although perhaps not optimal) test of the main trial hypothesis and will remain the primary analytic strategy, with these weighted log-rank tests serving as sensitivity analyses.

Separate proportional hazards models will also be used to compare the effects of methotrexate treatment on time to each of the individual components of the composite endpoint. The null hypothesis of no effect of methotrexate on an individual component will be evaluated by the logrank test, stratified on time since index MI and baseline diabetes status. Analyses will

use methods of competing risks survival analysis and compare the relative effects of randomized treatments on the different components of the composite outcome^{10,11}. The approach of Lunn and McNeil¹⁰ provides a readily accessible implementation of a classical approach to competing risk analysis developed by Kalbfleisch and Prentice¹².

While all primary and secondary endpoint analyses are on an intention-to-treat basis, CIRT is also functioning as a proof of concept trial and thus secondary analyses of those compliant with the respective LDM or placebo regimens will also be conducted. These analyses will use time-varying proportional hazards models, with an individual's level of adherence updated at each study visit. Adherence will be examined on a time-varying basis using a metric based on percent of study drug taken at last visit, such as half or more vs. less than half, and will also be analyzed cumulatively. Similar analyses will also be conducted on the basis of plasma levels of LDM metabolism.

We will explore in subgroup analyses whether treatment effects vary across categories of baseline covariates including age, gender, race, presence of diabetes or metabolic syndrome at baseline, index MI ≤ 6 vs > 6 months prior, baseline lipid levels, CHF at baseline, baseline inflammatory biomarker levels including high-sensitivity C-reactive protein, revascularization status, baseline background treatments including those known to affect adenosine, such as aggrenox, methylxanthines, and fioricet, nutritional measures related to adenosine function such as estimated daily total caffeine intake, and by plasma measures of LDM metabolism. Cutpoints for analyses will be determined after the final distribution of patients has been established.

Within each subgroup, we will use proportional hazards models to estimate the relative rate of the primary endpoint associated with active treatment versus placebo. Both crude analyses and models including limited baseline covariates will be fitted. To test for the significance of modification of treatment effects by a baseline characteristic, we will include interaction terms between this characteristic and treatment in the proportional hazards model, with statistical significance determined by a likelihood ratio test comparing models with and without the interaction terms between treatment and the categories of a specific covariate.

We will conduct these subgroup analyses regardless of whether or not the overall analyses of treatment effects are significant. Our approach to interpretation of subgroup analyses has always been very cautious and recognizes that, even in large trials, it is not likely to be possible to identify reliably subgroups of patients in whom treatment is especially effective or ineffective. In the absence of prior evidence for real heterogeneity, the overall trial result may provide the best evidence for the presence of a benefit in a subgroup¹³. Our approach thus corresponds to an informal empirical Bayes procedure in which effects in an outlying subgroup require interpretation in light of the overall treatment effect¹⁴.

The pre-specified secondary endpoints (all-cause mortality, primary endpoint plus coronary revascularization, hospitalization for congestive heart failure, primary endpoint plus all-cause mortality plus coronary revascularization plus congestive heart failure, net clinical benefit or harm, and new onset type 2 diabetes) will be evaluated using the same procedures described above for the primary endpoints. The net clinical benefit or harm endpoint will be presented as a table of the incidence of adverse events occurring with greater than 1% frequency in either treatment group, as well as a test of proportions for comparing the incidence in each treatment group. The overall rate of any serious adverse event during the randomized treatment period will also be compared between the methotrexate and placebo groups. Pre-specified tertiary endpoints will also be evaluated using the same procedures described for the primary endpoint.

Measures of quality of life and global health status, assessed at baseline, 1-year and closeout visits, will be analyzed in a mixed-effects linear regression model with subject as a random effect. Of particular interest in this model will be a time by treatment interaction. The

model will use two indicators of post-randomization (1-year and final visit) to evaluate a possible non-linear effect of treatment on outcomes by time.

To enhance interpretation for clinicians through consideration of absolute treatment effects, we will also estimate the number needed to treat or the number needed to harm, for both primary and secondary endpoints. Specifically, we will use the approach of Altman and Andersen¹⁵ to obtain these estimates based on the Kaplan-Meier estimates of time-specific treatment effects.

Longitudinal analyses will quantify the impact of methotrexate on biomarkers including lipid levels, inflammatory markers, creatinine, and change in HbA1c, with the latter analyses stratified by presence of diabetes at baseline. Additional longitudinal analyses will evaluate the time course of methotrexate treatment on important biomarkers of safety including serum creatinine and estimated glomerular filtration rate.

Mediation analyses exploring treatment effect differences by achieved reduction in inflammation and level of adherence to assigned treatment are also planned. Following approaches used in previous analyses of the relationship of changes in lipids and hs-CRP with effects of statin therapy on outcomes¹⁶⁻¹⁸, we will group subjects into achieved target levels of biomarkers and relate these achieved levels to treatment outcomes. This will also be combined with an analysis of compliance to explore whether observed treatment effects are compliance driven.

We also plan to evaluate whether genetic polymorphisms associated with vascular risk, inflammation, thrombosis, or LDM metabolism modify any benefits or risks of LDM on clinical outcomes observed in the trial.

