4.19. Trial Conclusion and Close Out Visits

At the close of the trial, all randomized participants will be asked to return to the local study sites to see a member of the physician's study team. Compliance, side effects, and patient contact information will be collected, and study end points will again be assessed by the local study staff. Therapy with study drug will be discontinued, and the patient's remaining

calendar packs of study drug will be collected. While no observational registry is currently planned, the Clinical Coordinating Center may request that local study sites approach study participants about enrolling in a post-trial observational registry.

To assess the impact of LDM withdrawal on diabetes incidence and glycemic control, participants will have one final laboratory evaluation for ascertainment of HbA1c 3 months after discontinuing study drug therapy.

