The primary endpoint of the trial is the time from randomization to the first occurrence of any component of the clinical composite endpoint including myocardial infarction, stroke and cardiovascular death. The primary analysis of the trial will use a likelihood ratio test based on a proportional hazards model stratified on time since qualifying event (≥ 6 months vs. < 6 months), type of event (myocardial infarction vs. multivessel coronary disease), and presence of either diabetes or metabolic syndrome to test the null hypothesis of no association between assignment to active methotrexate and the rate of the primary endpoint. All analyses will classify patients according to their randomized treatment assignment, i.e. according to the intention to treat principle, and will base evaluation of statistical significance on a two-sided test with level 0.05. Secondary analyses will further stratify on study site, although these analyses will likely be less efficient because of sparse strata that will arise because of small numbers of participants from some sites. The estimated relative hazard in the methotrexate group compared to the placebo group with an accompanying 95% confidence interval will quantify the treatment effect⁵¹. If this relative hazard is less than 1, then $100 \times (1 - \text{estimated relative hazard})$ will be defined as the percent reduction in hazard associated with methotrexate treatment.

Rates of occurrence of the primary endpoint will be defined as the total number of subjects who have this event in a treatment group per 100 person-years of follow-up, counting all time from randomization until the first of the event, death, end of trial, or withdrawal of consent. Estimates of the probability of the primary endpoint by time after randomization within treatment groups will be based on the method of Kaplan and Meier⁵². We will also use the proportional hazards model to control for baseline factors that might influence the rate of the primary endpoint (e.g. age, race, gender, baseline comorbidities, and concomitant medications), as control for these variables may yield more efficient estimates of relative treatment effects⁵³. If Kaplan-Meier plots of event free survival by study time, or related plots of $\log(-\log)(\text{survival})$, indicate violations of the proportional hazards assumption, or a formal test of trend in the scaled Schoenfeld residuals indicates such a violation, then weighted log-rank tests will be used

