1.3. Number of Subjects

Approximately 7,000 men and women from the United States and Canada will be enrolled. The trial is event driven such that in the absence of extreme effects, the trial will conclude after accrual of at least 530 primary endpoints, the number needed to provide 90 percent power to detect a 25 percent relative risk reduction with a conservative interim monitoring plan.

Sample size and power for CIRT have been estimated under several alternative assumptions about the rate of the primary endpoint in the placebo group and the likely reduction in this rate among those in the methotrexate group. All estimates are based on a two-sided log-rank test comparing the time to recurrence between two treatment groups at the 0.05 significance level. These estimates use the approach of Lachin and Foulkes under the assumption of a uniform hazard and to account for attrition due to drop-out¹. The following assumptions have been made:

- (a) Based on previous trials in individuals with a prior myocardial infarction, and considering the increased rate of major cardiovascular events associated with either diabetes or metabolic syndrome, it is expected that annual event rates will be between 3.25 and 4.0 per 100 person-years in the placebo group.
- (b) A clinically meaningful reduction in the rate of the primary endpoint is assumed to be in the range from 25% to 35%.
- (c) The recruitment period will be split into a ramp-up period, followed by steady-state randomization. Each randomized patient will be asked to continue blinded treatment until study completion.
- (d) As these patients have strong affiliations with their treatment centers and will have been tested in a run-in period, low rates of loss to follow-up are anticipated. Power calculations assume a 5% annual rate of loss to follow-up.

Under these assumptions Lachin and Foulkes show that the power of the trial with N total randomized subjects in the methotrexate and placebo groups combined is

$$Power = \Phi^{-1} \left(\sqrt{N} (\lambda_c - \lambda_e - 3.92 \sqrt{\Psi(\bar{\lambda})}) / (2\Psi(\lambda_e) + 2\Psi(\lambda_c))^{1/2} \right)$$

where Φ is the standard normal distribution function,

$$\Psi(\lambda) = \lambda(\lambda + .05) / (1 - [\exp(-2(\lambda + .05)) - \exp(-4(\lambda + .05))] / (2(\lambda + .05))),$$

λ_e is the incidence rate in the methotrexate group,

λ_c is the incidence rate in the placebo group

$$\bar{\lambda} = .5\lambda_e + .5\lambda_c$$

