5.2. DSMB Analyses

Interim analyses of rates of the primary outcome, as well as rates of the individual components of the composite endpoint, and the pre-specified secondary endpoints will be prepared for presentation to the Data and Safety Monitoring Board (DSMB). Reports to the DSMB will also include comparisons of baseline characteristics between treatment groups, displays of cumulative recruitment by study time, comparisons of post-randomization laboratory values by treatment group, and rates of adverse events, both overall and within systems, by treatment group. The frequency of the meetings will be determined by the independent DSMB appointed by the NHLBI.

Specifically, the blinded portion of the report will display, by treatment group and visit number, the number of subjects with an expected visit (i.e. those whose window for that visit closed at least 4 weeks before database lock for the particular interim report), the number and percent of those who remained on drug at that visit, and secondary tables which display the numbers of subjects who gave scheduled blood samples. An additional table will display by treatment group the numbers of subjects who remain in study and on drug, and, for those who have discontinued, the reason for discontinuation. Categories for reasons for stopping which we have used in the past are: Adverse Event, Endpoint, Deceased, Medication Use, Investigator Decision, Site Closure, Protocol Noncompliance, Lost to Follow-up, Withdrew Consent, Other, and Unknown. Additional tables will display, by treatment group and visit number, the rates of adherence based on self-reported pill counts. These last tables will be shown two ways: first, restricted to subjects who attended a visit, and then with 0 imputed for adherence for subjects who missed a visit and whose visit window closed more than 12 weeks before database lock for that interim report. Overall, power for the trial was estimated under the assumption of a 5% annual drop-out and loss to follow-up rate. If the rate exceeds this amount at a scheduled interim report, study power will be re-estimated based on the observed rate.

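### Are reported event rates biased because the person-time definition does not name loss to follow-up?

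*Combined protocol and SAP*

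**What the plan says.** Protocol 5.1 (Statistical Analysis) and SAP 4.3 (Efficacy) define the rate as participants with the event per 100 "person-years of follow-up, counting all time from randomization until the first of the event, death, end of trial, or withdrawal of consent". SAP 4.3 words this for any endpoint and carries the methods further: "Pre-specified tertiary endpoints will also be evaluated using the same procedures described for the primary endpoint".

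Loss is expected. SAP 1.3 states "Power calculations assume a 5% annual rate of loss to follow-up", and protocol 5.2 says the same. SAP 5.2 describes the same allowance more broadly: "power for the trial was estimated under the assumption of a 5% annual drop-out and loss to follow-up rate". The reasons for discontinuation in SAP 5.2 include "Protocol Noncompliance, Lost to Follow-up, Withdrew Consent, Other, and Unknown", so loss and withdrawn consent are separate categories.

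No section gives an explicit censoring date for a lost participant. At close-out (protocol 4.19) all randomized participants are asked back and "study end points will again be assessed by the local study staff".

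**The concern.** The definition says how time is counted and then names four stops. A participant who disappears without withdrawing consent meets none of them until the trial ends. A programmer working from the list alone could keep that person in the denominator for months or years in which no event could have been seen.

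The numerator would stay the same and the denominator would grow, so every person-year rate would be too low. A true placebo rate of 3.25, the bottom of the design range, would be reported below that range. Secondary and tertiary endpoint rates would be affected too, as would the rates by arm that go to the DSMB. Because SAP 5.2 separates loss from withdrawn consent, the first cannot simply be taken to fall under the second.

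**Working it through.** **Inputs.** Placebo rate λ = 0.0325 to 0.04 a year, attrition hazard η = 0.05, constant hazards, 3500 per arm, hazard ratio 0.75 and follow-up of 2 to 4 years (protocol 5.2; SAP 1.3), with follow-up taken as uniform over that span. The documents do not split the 5% between loss and withdrawn consent, so the loss share s is varied as an assumption.

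**1. Reproduce the plan's event count.** With a = λ + η, mean observed time per participant is

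m = (1/a) × {1 − [exp(−2a) − exp(−4a)]/(2a)}, and expected events per arm are 3500 × λ × m.

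- Placebo, λ = 0.0325: a = 0.0825, m = 2.647 years, 301.1 events.
- Methotrexate, λ = 0.024375: a = 0.074375, m = 2.679 years, 228.5 events.
- Total 529.6, against 529 in the plan. At a placebo rate of 4.0 the total is 645.4, against 645.

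This m stops each participant's clock at loss. With attrition set to zero, the count at 3.25 would be 571. So the plan's own arithmetic ends observation at loss.

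**2. Literal reading.** A participant lost at time u is credited with the remaining T − u years, where T is the planned end of follow-up. Averaged over T, the added time is

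extra = (s × η / a) × (3 − m).

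Placebo at 3.25 with s = 1: (0.05/0.0825) × (3 − 2.647) = 0.214 years, so the denominator becomes 2.861 years. Events are unchanged, so the reported rate is 3.25 × 2.647/2.861 = 3.01, which is 7.5% low. The proportion lost is 0.05 × 2.647 = 13.2%.

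| Loss share s (assumed) | Mean time counted, years | 3.25 reported as | Shortfall |
|---|---|---|---|
| 100% | 2.861 | 3.01 | 7.5% |
| 75% | 2.807 | 3.06 | 5.7% |
| 50% | 2.754 | 3.12 | 3.9% |
| 25% | 2.700 | 3.19 | 2.0% |
| 10% | 2.668 | 3.22 | 0.8% |

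At a placebo rate of 4.0 and s = 1, the reported rate is 4.0 × 2.618/2.830 = 3.70, again 7.5% low.

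**3. Later ascertainment.** Take s = 1 and suppose half of the lost participants have their status recovered at close-out (an assumption). Unresolved loss then has hazard 0.025, a = 0.0575, m = 2.748 and extra = (0.025/0.0575) × (3 − 2.748) = 0.110. The reported rate is 3.25 × 2.748/2.857 = 3.13.

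**4. Comparison between arms.** Methotrexate at s = 1: 2.4375 × 2.679/2.895 = 2.256. The ratio is 2.256/3.007 = 0.750, unchanged. The crude difference falls from 3.25 − 2.44 = 0.81 to 3.007 − 2.256 = 0.75 per 100 person-years. The plan does not set that difference as an analysis.

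**5. What the plan means by follow-up.**
- Protocol 5.2 and SAP 1.3 give the 2-to-4-year span only for participants who are neither censored nor have an event. Those who are censored, including the lost, therefore have less follow-up.
- SAP 2.1 admits to the ITT set only randomized participants who have some follow-up data.
- SAP 4.4 describes people who have left randomized treatment but are still being followed, so follow-up means continued observation and not mere membership of the trial.

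Read this way, time after last contact is not person-time of follow-up, and the four stops apply within the observed period. The extra time in step 2 is zero.

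**The case for a change.** The strongest contrary argument is that a prespecified definition should permit only one program. Here one analyst can follow the list and another the unit, and both can claim compliance. The plan can be explicit when it chooses: SAP 5.2 gives a missed-visit rule for adherence but nothing comparable for endpoint time. If loss differed between arms, the literal reading would also move the crude ratio. With an assumed 6% a year on methotrexate and 4% on placebo, all of it loss, a true ratio of 0.750 would appear as about 0.728 and a true 1.00 as about 0.970.

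The omission stands, and so does the arithmetic. The practical consequence does not. The literal reading requires an analyst to count unobserved time as follow-up, against the plan's usage and its power formula. Stopping the clock at last observation is also the ordinary convention for the Cox, log-rank and Kaplan-Meier analyses, for which the plan gives no separate rule. The interim boundaries are set on Z-values, P-values and the relative hazard, not on a ratio of crude rates. SAP 5.2 shows the DSMB discontinuation and its reasons by treatment group and re-estimates power if attrition exceeds 5%, so heavy or uneven loss would be seen.

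A phrase added to the definition would also need care: vital status may be known later than MACE status, so one last-contact date would not suit every endpoint.

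**Conclusion.** No change is needed. The list does leave out loss to follow-up, but the sentence counts follow-up, and the plan's own usage and its reproduced event count treat that as observed time. On that reading the rates are unbiased. Only a strictly literal reading lowers them, by between 0% and 7.5%. The upper end assumes constant hazards, 2 to 4 years of follow-up, all of the 5% a year being loss and no status recovered later. Figures in between depend on a split that the documents do not give.

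Even at the upper end, equal loss leaves the rate ratio at 0.750. The stratified primary test and the Kaplan-Meier-based number needed to treat in SAP 4.3 are not governed by this definition. The end of the trial and the timing of the interim looks depend on event counts. What remains is a detail that a competent analyst settles when deriving the censoring date.
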